indicated a small, statistically significant overall effect for CBTs (Hedges's $g = 0.08$) that was not significantly better than a comparator when examining RCTs alone ($g = 0.04$). Although results in aggregate reveal a mostly disappointing outcome for CBTs in resolving caregiver distress across conditions, a more careful examination of findings reveal commonalities shared by the few studies in each meta-analysis that achieved stronger effects. For instance, in dementia caregivers, CBTs combined with yoga and relaxation⁹⁸ offered comparatively greater efficacy. Similar findings emerged among caregivers for autism-spectrum patients with CBTs with mindfulness and acceptance components, which involve learning skills to maintain a present-focused attentional stance and non-judging attitude of momentary thoughts and emotions that arise.⁹⁷ Among cancer caregivers, promising but preliminary findings for an acceptance- and mindfulness-infused CBT are emerging from Co-I [name]'s group as well.⁹⁹ Taken together, the plight of caregivers is complex and likely requires a comprehensive intervention that considers all factors inherent in the caregiver experience that may not be fully captured in traditional CBT or purely burden-focused psychoeducational approaches.

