We will test differential effects of ERT-C versus CBT-C using separate GLIMMIX/HLM for each outcome (e.g., depression, anxiety). For HADS outcomes and for rumination and worry post-intervention outcomes, the *i*th caregiver, within the *j*th site, at the *k*th timepoint will be regressed on a time variable, an indicator for ERT-C arm, and time-by-arm interaction. That is, baseline assessments will be included as an outcome and not a covariate. This flexible analytic strategy will allow testing of non-linear time effects, treatment differences immediately post-treatment, and comparison of 6-month maintenance, all within the same model framework via specific contrasts. This strategy also utilizes all complete assessments, such that caregivers who miss data at a subset

of time points will still be included and analyzed in the model. Random per-caregiver and per-site intercepts will control for intraclass correlation introduced by repeated measures and cluster effects, which is an important statistical consideration in choosing GLIMMIX/HLM as our primary statistical approach. Prior to regression modeling, transformations to the outcome will be made as necessary and based on tests of parametric assumptions. A significant finding on the test of the interaction term would be evidence that there is a differential reduction in the outcome by treatment assignment. For immediate gains, data will be restricted to T1 to T2 (including the mid-intervention assessments for HADS outcomes). For 6-month maintenance, a similar model will be used, restricted to the post-intervention data. For HADS outcomes pre to post intervention, 10 assessments (T1, T2, and 8 mid-intervention timepoints) are expected; for all 4 primary outcomes, 3 timepoint assessments (T2, T3, T4) are expected for 6-month maintenance. A significant finding on the main time effect would indicate a change in outcomes during the 6-month follow-up for CBT-C participants, and a significant finding on the interaction coefficient would indicate a significantly different change in follow-up outcomes between ERT-C and CBT-C. Superiority is defined by a significant finding on post-treatment difference (T1 to T2) and either further significant differentiation post-intervention (T3 to T5) or no statistically significant differentiation if the CBT-C group converges with the ERT-C group during this time.

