Rumination and Worry (Pre to Post) and Patient Outcomes: For rumination and worry pre to post intervention, only 2 assessments (T1 and T2) are collected. Patient outcomes are only collected at baseline (T1) and 3-months post-treatment (T3). Rather than test for a time-treatment interaction effect, differential change will simply be tested as the main group (ERT-C vs. CBT-C) effect in an HLM model of change scores regressed on this main effect and with a random per-site intercept, separately for each outcome (i.e., caregiver rumination, caregiver worry, patient outcomes).

Exploratory Analysis - Potential Moderators: As we move into the era of precision medicine and person-centered mental health care,[197] it is necessary to examine caregiver-specific factors that may moderate impact of ERT-C so that we may build a foundation for a targeted approach to addressing caregiver anxiety and depression. The impact of moderators of psychosocial interventions among patients with cancer has received increasing attention[198], with growing evidence for the influence of age and cancer type on various psychosocial outcomes. Therefore, putative moderators of therapeutic efficacy, including cancer site, cancer stage, and caregiver sociodemographic factors, will be assessed within this same HLM framework for Aim 1. Longitudinal change scores for each outcome at each major time point (i.e., T2, T3, T4) will first be calculated. Next, potential moderators will be included in separate HLM models, where each model regresses the change score on main effects for ERT-C and the moderator, plus an interaction of the two. The HLM structure will account for clustering effects of the sites only, as change scores are assessed individually and thus a single observation per participant.

Attrition and Missing Data. We computed sample size estimates anticipating 20% attrition. Based on previous trials at MSK and MGH with caregivers, missing data should be less than 20% by T3. Missing data rates and attrition will be compared between treatment arms, and also by pre-intervention measures.

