Power and Sample Size for Aim 1. Preliminary data found ERT-C to have a pre-treatment to post-treatment effect size of $g=0.49$ on depression and anxiety. A recent meta-analysis found very small ($g=0.08$) effects of CBT on these outcomes; this implicates a differential effect size of $d=0.41$. Using an HLM model with up to 3 time points, a within-subject ICC of 0.2, allowing for approximately 20% attrition, and setting Type I error to the conservative value of 0.0125 to account for 4 primary outcomes, we simulate 90.4% power for the differential pre-treatment to post-treatment changes for Aim 1 if the effect size is at least $g=0.41$ and 82.8% power for a more conservative effect of $g=0.37$. Power was simulated using the *simr* [199] package in R. For patient outcomes, the PI anticipates at least 50% enrollment of patients associated to the caregivers, and comparable attrition between patients and caregivers. Enrollment of 120 patients, with 80% retention at the 3-month follow-up assessment will provide 80% power to detect a standardized effect of at least $d=0.63$ for the difference in change scores using an independent samples t-test approximation at alpha of 0.05. Similarly for rumination and worry from pre to post intervention, enrollment of 240 caregivers with 10% attrition during intervention will provide 80% power to detect a medium effect of at least $d=0.50$ with alpha of 0.0125 for these two primary outcomes.

AIM 2: Attention and Metacognitive Regulation Will Have Indirect Effects on the Primary and Secondary Outcomes. Growth curve models will assess overall effects of treatment on primary and secondary outcomes, and the partial mediation of primary outcomes via attention and metacognition regulation skills increases and whether this effect will be more pronounced in ERT-C compared to CBT-C.

Hypothesis 2a: Only skills that specifically target components of distress (i.e., attention regulation, metacognitive regulation) will mediate primary and secondary caregiver outcomes compared to other facets of improving the caregiving experience (i.e., reducing perceived burden, maladaptive behavioral coping).

Hypothesis 2b: These gains and mediation in attention and metacognitive regulation will be more pronounced in caregivers receiving ERT-C as compared to CBT-C.

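### The 90.4% and 82.8% power quoted for Aim 1 belongs to a three-visit model that is none of the planned pre-to-post tests; for HADS the true figure turns on an unstated SD unit, and for worry and rumination the headline is not reached

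*Combined protocol and SAP*

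**What the plan says.** The power paragraph for Aim 1 in Section 14.0 describes its simulation as "Using an HLM model with up to 3 time points, a within-subject ICC of 0.2", with about 20% attrition, "setting Type I error to the conservative value of 0.0125 to account for 4 primary outcomes". From this it states "we simulate 90.4% power for the differential pre-treatment to post-treatment changes for Aim 1 if the effect size is at least" 0.41, and 82.8% at 0.37.

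The 0.41 is a subtraction. The first term is given as "Preliminary data found ERT-C to have a pre-treatment to post-treatment effect size of $g=0.49$ on depression and anxiety". The second is a meta-analytic CBT effect of 0.08. Section 3.0 describes that 0.08 as the overall pooled effect and adds that CBT was "not significantly better than a comparator when examining RCTs alone" (g = 0.04).

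The planned tests are set out just before the power paragraph:

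- **HADS anxiety and depression** (Aim 1, Primary Analyses): a model with time, arm and time-by-arm terms and random caregiver and site intercepts, restricted to T1-T2 for immediate gains. "For HADS outcomes pre to post intervention, 10 assessments (T1, T2, and 8 mid-intervention timepoints) are expected".
- **Worry and rumination**: "For rumination and worry pre to post intervention, only 2 assessments (T1 and T2) are collected". The test is the group effect on the change score.

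Three occasions (T2, T3, T4) appear only in the 6-month maintenance model. The power paragraph also gives worry and rumination their own sentence: 80% power at d = 0.50, alpha 0.0125, 10% attrition.

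**The concern.** The figure that justifies 240 caregivers should be the power of the tests that decide the trial. Here the simulated model has a number of visits that no planned pre-to-post test has. Because the figure is offered for Aim 1 as a whole, with alpha split over four outcomes, a reader may take it to cover all four. If the planned tests have materially different power, the trial goes ahead on an assurance that was never computed for it, and a null result on any one outcome will be hard to interpret.

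The planning effect raises a second question. A within-arm pre-to-post effect includes improvement that would also occur in the comparator arm; a comparison against controls does not. Subtracting one from the other gives a between-arm difference only if both are of the same kind.

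**Working it through.** **Inputs from the plan.** 240 caregivers, 1:1; 20% attrition gives 96 per arm, 10% gives 108; ICC 0.2; alpha 0.0125; effects 0.41 and 0.37. **Assumptions.** Two-sided test (z = 2.498); total SD 1 at each visit; equal correlation 0.2 between visits; no random slopes or site variance; for HADS, equally spaced assessments and a linear effect that reaches the stated size at T2.

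Power = Φ(d/SE − 2.498). Results are given as power at 0.41 / power at 0.37.

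**1. Reproducing the stated pair.** Three visits, baseline means constrained equal (no arm term), one constant effect at two post-baseline visits. Variance factor = (1 + 0.2)/2 − 0.2² = 0.56. SE = √(2 × 0.56/96) = 0.108.
- 0.41/0.108 − 2.498 = 1.30, power 90.3%.
- 0.37/0.108 − 2.498 = 0.93, power 82.3%.

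A 20,000-run simulation of this model gives 90.5% / 82.7%, against the stated 90.4% / 82.8%.

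**2. Same three visits with the planned arm term.** The contrast is now the mean of two follow-ups minus baseline: variance 1 + 0.6 − 2 × 0.2 = 1.2, SE = √(2 × 1.2/96) = 0.158. Power 54% / 44%.

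**3. Other three-visit layouts.** A linear trend with the arm term gives 40% / 32% if the effect is reached at the last visit, and 98% / 94% if it accrues in each interval. Neither matches. A four-visit layout with the arm term, gradual 20% dropout and change-SD units also comes close (90.2% / 82.1%), but it has more visits than the plan states. The near-match in step 1 therefore does not settle which SD unit was meant.

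**4. Planned HADS test.** Ten occasions scaled 0 to 1: the sum of squared deviations is 82.5/81 = 1.0185. SE = √(2 × 0.8/(96 × 1.0185)) = 0.128.
- Raw-SD units: 0.41/0.128 gives 76%; 0.37/0.128 gives 65%.
- Change-SD units: the SD of a T1-T2 change is √(2 × 0.8) = 1.265, so the effects become 0.519 and 0.468. Power 94% / 88%.

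With gradual 20% dropout, retaining earlier visits, the raw-SD figures are 80% / 70%; with no attrition they are 86% / 77%.

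**5. Planned worry and rumination test.** Two-point change score, 108 per arm.
- Change-SD units: SE = √(2/108) = 0.136; by the t-test, 69% / 58% (normal approximation 70% / 59%).
- Raw-SD units: SE = √(2 × 1.6/108) = 0.172; power about 45% / 36%.
- No attrition (120 per arm), change-SD units: at most 75% at 0.41.
- The plan's own sentence, d = 0.50 in change-SD units: 87.5% at 108 per arm and 82.6% at 96. The claimed 80% is met.

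| Test | Raw-SD units | Change-SD units |
|---|---|---|
| Stated headline | 90.4% / 82.8% (unit not stated) | |
| HADS, 10 assessments, 96 per arm | 76% / 65% | 94% / 88% |
| Worry, rumination, 108 per arm | 45% / 36% | 69% / 58% |

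**6. The planning effect.** 0.49 − 0.08 = 0.41. With the RCT-only figure from Section 3.0, the same subtraction gives 0.49 − 0.04 = 0.45. Section 3.0 reports both a within-subject open trial of ERT-C (0.4 to 0.9) and a between-subject waitlist trial (0.5 to 1.0); the power paragraph does not say which one supplied 0.49.

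**The case against.** Four stronger readings are tempting, and the documents do not support them.

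*That 90.4% is a miscalculation.* It is nearly reproduced with the stated ICC, alpha and attrition. The fault is that the powered model is not a planned test.

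*That the HADS outcomes are underpowered.* This holds only in raw-SD units. The patient-outcome sentence in the same paragraph expresses its effect as a difference in change scores, so change-SD units are a live reading, and on that reading the planned HADS test exceeds both stated figures.

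*That two of the four primary outcomes are below 80% at the plan's own effect.* The 0.41 is derived from depression and anxiety. Worry and rumination have a separate planning effect of 0.50, for which the stated power is correct and slightly conservative. What stands is that the Aim 1 headline does not extend to them, and that their power at 0.41 and 0.37 is not given.

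*That 0.41 is shown to be inflated.* Neither the source design of 0.49 nor the mix of designs behind 0.08 is given, and using the RCT-only value would raise the difference to 0.45. What stands is that like-for-like subtraction has not been shown.

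It is also fair to say that neither the sample size nor the analysis need change.

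**Conclusion.** The point holds as a mismatch between the test that was powered and the tests that are planned. The stated 90.4%/82.8% describes no planned T1-T2 test, and the three-visit model that nearly reproduces it falls to 54%/44% once the planned arm term is added. For HADS, whether power is below or above the headline depends on a unit that the plan leaves out. For worry and rumination, the headline fails on either unit, while their own d = 0.50 statement stands. The 0.41 is a planning assumption and not an estimate of the between-arm difference.

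The sizes rest on the two-sided alpha, equal-correlation structure and linear HADS effect listed in the check. The mismatch in visits rests on the text alone. A power statement on which the trial relies is wrong as written and should be corrected.

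**What to change.** Re-run the simulation with the models in Section 14.0 and report power by outcome:

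- HADS: ten T1-T2 assessments, with the planned arm term and random intercepts. Limit any replacement for 90.4%/82.8% to HADS.
- Worry and rumination: two-point change score. Keep the d = 0.50 sentence and add power at 0.41 and 0.37 (69% and 58% in change-SD units at 10% attrition).
- State the SD unit of d and the correlation used.
- Describe 0.41 as a planning assumption, give the source design of 0.49, and delete *implicates*.

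Random slopes and a therapist effect are not in the planned model; they are optional sensitivity runs. The cost is one simulation re-run and possibly a less favourable stated figure, with no added enrolment.

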Primary Analyses: We will assess gains in emotion regulation as well as reductions in anxiety and depressive symptoms via growth curve modeling. First, for both emotion regulation skills and outcomes, a series of traditional growth curve models will assess the effect of ERT-C (versus CBT-

[figure not shown]

Figure 2. The parallel process latent growth curve model for mediation of ERT-C on outcomes via emotion regulation skills (measured weekly).

C) on each potential mediator from the ACS, EQ-D, ERQ-R, and COPE instruments which are assessed weekly during the intervention. Next, for each outcome, similar growth curve models will be used to assess the overall effect (direct and indirect effects) of ERT-C on outcomes both during the intervention and at major timepoints. We will employ parallel process latent growth curve modeling (PP-LGCM [200]) to assess the mediational process provided by weekly data. In PP-LGCM, changes in potential mediators and changes in outcomes are both modeled in a single measurement model. This combination of growth curve methodology with structural equation

modeling efficiently utilizes the longitudinal data of both the mediators and outcome variables and is depicted for the single mediation variable case in Figure 2. Here, η_1 and η_3 represent the intercepts for the growth processes for the mediation and outcome measures, respectively; η_2 and η_4 represent the slopes for the mediation and outcome measures, respectively. Means for mediators and outcomes may be impacted by intervention and correlated. Trajectory of a mediator may be impacted by treatment and baseline outcome. Trajectory of the outcome may be impacted by treatment and with both baseline and trajectory of the mediator. The mediation hypothesis is supported if the product of α and β is significant [201], that is, if ERT-C drives change in the mediator and change in the mediator drives change in the outcome. This analysis will be conducted using M-Plus software.

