Power and Sample Size for Aim 2. Statistical power for mediation models was estimated from simulations by Fritz and MacKinnon, [202] which provide conservative estimates given the reduction in noise provided by our weekly assessments and growth curve modeling. Allowing for up to 20% attrition, the sample will provide at least 80% power to detect mediation using the Sobel test if one of the two paths (α or β) has a small-medium effect size (Cohen's $d=0.39$), and the other has at least a small effect ($d=0.26$).

Aim 3: Differential Effects of Treatment on Change in Biomarkers. We will describe and test differential changes in inflammation and salivary biomarkers overall and by treatment arm.

Hypothesis 3a: ERT-C will result in greater reductions in cortisol dysregulation and systemic inflammation as compared to CBT-C and gains will be maintained at 6-months follow-up.

Exploratory Hypothesis 3b: Reductions in cortisol dysregulation and systemic inflammation observed with ERT-C will be most prominent in caregivers with baseline elevations in distress.

Primary Analyses: The same HLM/GLIMMIX framework from Aim 1 will be used for Aim 3. Transformations may be needed for both biomarkers. The analysis will be similarly conducted to assess both differential pre-post change (T1 to T2) and also maintenance at 6-months follow-up (T2 to T4), using appropriate contrasts on the time variable. This same framework will allow for testing the exploratory moderation hypothesis. Specifically, for Hypothesis 3b, outcomes will be regressed on the ERT-C indicator, an indicator of elevated baseline distress, and the interaction of the two. A significant finding on the interaction term will be evidence to a moderation effect and will be followed with stratified analyses of the biomarker outcomes by baseline distress category and treatment arm.

Power and Sample Size for Aim 3. Based on previous participation rates with biological samples at our institutions, we anticipate at least 75% of the 240 enrolled caregivers to provide samples. With a conservative 20% attrition assumption, an analytic sample of $n=144$ would provide 80% power to detect a small-medium effect size of $d=0.36$ for the t-test for Hypothesis 3a.

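### Hypothesis 2a claims that only the targeted skills mediate, but Aim 2 specifies no test comparing targeted with rival indirect effects

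*Combined protocol and SAP*

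**What the plan says.** Hypothesis 2a appears in Section 2.0 and again in Section 14.0 under Aim 2: "Only skills that specifically target components of distress (i.e., attention regulation, metacognitive regulation) will mediate primary and secondary caregiver outcomes". The comparison is with other facets of the caregiving experience, "i.e., reducing perceived burden, maladaptive behavioral coping".

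The Aim 2 Primary Analyses fit growth curves to each candidate mediator from the ACS, EQ-D, ERQ-R and COPE. They then fit a parallel process latent growth curve model in M-Plus, which "is depicted for the single mediation variable case in Figure 2". The decision criterion is: "The mediation hypothesis is supported if the product of α and β is significant".

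The Aim 2 power paragraph says that, after up to 20% attrition, "the sample will provide at least 80% power to detect mediation using the Sobel test". The paths assumed are 0.39 for one and at least 0.26 for the other, both labelled as d. No significance level is given for Aim 2. The Aim 1 power paragraph refers to "setting Type I error to the conservative value of 0.0125 to account for 4 primary outcomes".

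On measurement, Section 11.0 has the ACS, EQ-D, ERQ-R and the COPE Active Coping subscale completed before every session. Burden (CRA) is collected at T1 to T4 only, and not from bereaved caregivers.

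**The concern.** Hypothesis 2a makes two statements: the targeted skills mediate, and the rivals do not, or do so less. The criterion in Aim 2 addresses the first. No contrast of indirect effects, bound on a rival's effect or model holding several mediators together is specified for the second. Anyone applying the plan as written would have only a table of significant and non-significant products from which to argue specificity.

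That split is not evidence of a difference. It also rewards weak measurement of the rival: the less power there is to detect the rival, the more likely it is to look inert. This is relevant because burden is measured at four timepoints, while the targeted skills are also measured at every session.

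The specificity of the mechanism is the scientific content of Hypothesis 2a. A non-specific pathway could be reported as a specific one.

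**Working it through.** **Inputs.** From Section 14.0: 240 caregivers, 1:1 allocation, 20% attrition, so n = 240 × 0.80 = 192; paths 0.39 and 0.26; stated power at least 80%. Assumed: two-sided alpha of 0.05, with 0.0125 as a sensitivity value, and correlation between mediators from 0 to 0.5. The documents give neither for Aim 2.

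**1. The plan's own power figure.** Sobel z = ab / √(a²·se_b² + b²·se_a²), with power = Φ(z − 1.96).

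- *Paths read as coefficients on unit-SD predictors* (se_a = se_b = 1/√192): z = 0.1014 / √((0.1521 + 0.0676)/192) = 3.00, power 0.85. The stated floor of 80% is met.
- *Treatment path read literally as Cohen's d between equal arms* (se_a = 1/√(192 × 0.25) = 1/√48): with a = 0.39 and b = 0.26, z = 0.1014 / √(0.1521/192 + 0.0676/48) = 2.16, power 0.58. With the paths swapped, z = 1.71, power 0.40. The floor is not met.

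**2. What the split does when target and rival are identical.** If each is detected with probability p and the tests are independent, the rival is missed with probability 1 − p. The split (target significant, rival not) has probability p(1 − p).

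| Basis | Power p | Rival missed | Split |
|---|---|---|---|
| Plan's stated floor | 0.80 | 20% | 0.80 × 0.20 = 16% |
| Coefficient reading | 0.85 | 15% | about 13% |
| Coefficient reading, alpha 0.0125 | 0.69 | 31% | 21% |
| d reading, a = 0.39, b = 0.26 | 0.58 | 42% | 24% |
| d reading, a = 0.26, b = 0.39 | 0.40 | 60% | 24% |

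Above p = 0.50 the product falls as p rises. Power of at least 80% therefore makes 20% and 16% upper limits. For one independent pair the split can never exceed 25%.

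**3. Simulation.** One target and one rival had identical paths, n = 192 and alpha 0.05. Ordinary mediation regressions stood in for the latent growth model, whose variances the plan does not give.

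- *Coefficient reading, separate mediator models:* rival missed in 0.2% to 9.5%, split in 0.2% to 9%.
- *Coefficient reading, joint model, each product tested singly:* missed in 7.5% to 18%, split in 7% to 17%.
- *d reading, a = 0.39 and b = 0.26, separate models:* missed in 46% (uncorrelated) or 30% (correlation 0.4), split in 25% or 15%. Across both path orders and both model types, the split ranges from 14% to 25%.
- *Direct contrast a₁b₁ − a₂b₂ in a joint model:* wrongly favours the target in 1.4% to 2.3%.

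**4. What the contrast can detect.** With target paths 0.39 and 0.26:

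| True state of the rival | Coefficient reading | d reading |
|---|---|---|
| No effect on either path | 82% to 91% | 40% to 49% |
| Responds to treatment, no effect on outcome | 39% to 63% | 20% to 39% |

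**The case against.** The strongest reply is that the documents do not contain the faulty rule. A reader might infer that the plan will declare *only* from a non-significant rival. No section says so, and the hypothesis's wording of comparison could mean a formal one that was never written down. Nor does the text say that mediators will be fitted only one at a time: it describes what a figure depicts. Both points stand. What remains is that no comparison is defined, so one has to be supplied whatever was intended.

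A reader might also infer that an equal rival would be missed, and *only* falsely declared, in a large share of trials. The documents do not support that as a general statement:

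- Missing the rival and obtaining the split are different events, because the split also needs a significant target.
- The larger rates arise when 0.39 and 0.26 are taken as Cohen's d. On the coefficient reading, where the plan's 80% holds, separate models give a split in at most about 9%.
- The rates are for one pair on one outcome. Hypothesis 2a names two rival facets. If both were equal to the target and both had to be missed, independence at 80% power gives 0.80 × 0.20 × 0.20 = 3.2%.

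The COPE Active Coping subscale should not be treated as the rival in question either. Hypothesis 2a names burden and maladaptive coping, and this subscale measures neither.

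Finally, this is a mechanistic aim. It does not touch the superiority criterion in Section 13.1 or the Aim 1 analyses.

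**Conclusion.** The concern holds as a missing specificity test. Hypothesis 2a asserts a difference between mediators, and Aim 2 tests each mediator against zero only.

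On the plan's stated power, an identical rival would be missed in up to 20% of trials. The misleading split would arise in up to about 16% for one independent target–rival pair on one outcome. With separate models, the simulated split is under 1% to about 9% on the coefficient reading and about 15% to 25% on the literal Cohen's d reading. A direct contrast errs in about 2%. These figures rest on an assumed two-sided 0.05, assumed mediator correlations and a regression stand-in for the growth model.

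The size is therefore uncertain, but the gap does not depend on it. The named rivals are also poorly placed for any comparison: burden is not among the listed mediators and has no session-level data, and no listed mediator measures maladaptive coping. The point merits correction but does not threaten the primary result.

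**What to change.** In the Aim 2 Primary Analyses:

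1. For each outcome, pre-specify one joint model containing the targeted and rival mediators. Test the difference between their standardized indirect effects with a bootstrap confidence interval in M-Plus.
2. Conclude that a targeted skill mediates more strongly than a rival only if that interval excludes zero. Reword *only* in Hypothesis 2a to match.
3. State that a non-significant rival is not evidence of no mediation.
4. Include the rivals that Hypothesis 2a names. Add burden (CRA) to the mediator list and say how its T1 to T4 data enter the model. Name a measure for maladaptive coping, or drop that facet from the hypothesis, since COPE Active Coping does not measure it.
5. State the significance level for Aim 2, and whether 0.39 and 0.26 are coefficients or Cohen's d.

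Apart from any new coping measure, this uses data and software already planned. The contrast has modest power, so the specificity claim will be made less often. A joint latent growth model with several mediators is also a heavier fit at n = 192 than single-mediator models.
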